14. RECRUITMENT

14.1. Patient Identification

Potential participants will be identified by their existing medical team from acute medical units, LVP day units, outpatients and Gastroenterology/ Hepatology wards as potentially eligible. If patient is willing to hear more about the study they will then be approached by the research team. The research team will discuss the study in detail and provide the participant information sheet. The patient can then take their time to think about their participation and ask any questions they may have.

14.2. Consent

Participant consent

Potential research participants will be identified by the direct medical care teams at the participating sites and highlighted to the research teams. If the CI/PI is the usual consultant, then to avoid any potential conflict of interest these patients will be discussed either at multidisciplinary meetings (MDM) and/or referred to local transplant centres to ensure that liver transplant/TIPS is not an option. The participant information sheet (PIS) will be provided to the potential participant by a member of the research team and any questions addressed. After the participant has had time to read the PIS, the research team will meet up/call (dependent on patient preference) the potential participant/informal caregiver again and any further queries will be clarified. If the participant is willing then written informed consent will be received by the research team to participate in the main study. Participants will also have the opportunity to participate in an interview (optional) and to consent to an optional additional 20ml of blood to be taken and stored until the end of the study. Permission will also be received for participant contact details to be given to the qualitative researcher and if willing, the qualitative researcher will contact the patients directly.

A letter will be sent to the patient's GP informing them of their participation in this study.

Participants Who Lose Capacity During the Study

England

This is an end of life cohort with advanced liver disease. Such patients can be confused due to multiple reasons including hepatic encephalopathy. Capacity can fluctuate in this cohort. At each visit the participant's capacity will be checked using a capacity to consent checklist. If it is deemed that the participant lacks capacity then a Consultee will be approached. This can either be the participant's caregiver (personal Consultee) or if no caregiver is available, then the patient's independent medical consultant (nominated Consultee). The Consultee will be approached to advise whether participation in the trial is in the patient's best interest and provide written confirmation of this.

Scotland

In Scotland, once a patient gives consent then that remains valid for the remainder of the study. However, at the time of the initial consenting process, patients will be asked as to how they wish to proceed in case they lose capacity during the study. They can consent to either continue or withdraw from the study, and also whether their previously collected data can remain in the study.

Caregiver Consent

For all patients, potential informal caregivers (e.g. a friend or family member) will be identified if available. However, absence of a caregiver will not preclude participation in this trial. The informal caregiver will be approached with the patient's permission but both patient and caregiver do not need to take part together. Informal caregivers will be approached by the research team and an information sheet provided for participation in a questionnaire study assessing impact on caregivers. Written consent will be requested to participate in the questionnaire study. Informal caregivers will also have the opportunity to participate in an interview (optional). Permission will also be requested for caregiver contact details to be given to the qualitative researcher and if willing, the qualitative researcher will contact the caregiver directly to discuss further.

Healthcare professional (HCP) consent

HCPs (gastroenterologists, hepatologists, hospital and community nurses) will also be approached by the research team and given an information sheet to participate in an optional interview. Consent will be sought for their contact details to be passed on to the qualitative researcher, and if willing, they will be contacted directly by the qualitative researcher to discuss this further.

Screening Visit

Potential eligible patients will be invited to attend for an appointment. They will have the opportunity to ask questions about the study and written consent will be received. Routine bloods and assessments will be conducted in line with Table 3 Schedule of Assessments.

15. THE RANDOMISATION SCHEME

Randomisation, set up by the Brighton and Sussex CTU (BSCTU) statistician on Sealed Envelope[™], will be performed online by a research team member on a 1:1 basis to either LTAD or LVP (current standard of care), minimised on gender and liver prognostic scores (Child Pugh Score).

15.1. Allocation Sequence Generation

The random allocation of patients to treatments will be restricted by minimising on Child-Pugh Score (CPS) (>10 vs. \leq 10) and gender (male/female) with an 80% probability of allocating to the arm, which minimises the imbalance. This will achieve near balance across interventions on disease severity and gender (the majority are expected to be male).

15.2. Allocation Concealment Mechanism

The allocation sequence will be generated dynamically, with a random element as described above. This way, the next allocation will only be generated and become known upon actioning a request from a member of the clinical research team.

REDUCe 2 protocol v2 20.06.22

15.3. Implementation

Randomisation will be implemented using Sealed Envelope[™]. Patients will be enrolled by the research team who will log into the web-based system, enter patient ID number, recruiting site, gender and Child-Pugh Score. The system will automatically generate a confirmation email informing the research team of the allocation, a copy being sent to the BSCTU.

15.4. Blinding

Due to the nature of the intervention, there can be no blinding in this trial except of the trial statistician who will be kept blind until completion of the analysis by means of dummy labelling of the trial groups.

15.5. Notification of Randomisation

Randomisation can occur up to 10 days prior to the baseline visit. If it occurs prior to the baseline visit, the participants will be informed of their randomisation outcome via a telephone call from a member of the research team. In this call they will inform patients about which arm of the study they have been allocated to, and what to expect when they attend hospital for their baseline visit.

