13. STUDY PROCEDURES

13.1. Schedule of Assessments

Table 3. Schedule of Assessments

		1		1		1	1	1	1
	Screening	Telephone call	Baseline / WO (7 +/- 3 days post screening)	W2 (+/- 3 days)	× W4 (+/- 3 days)	WG (+/- 3 days)	W8 (+/- 3 days)	W10 (+/- 3 days)	W12 (+/- 3 days)
Perform capacity check using capacity checklist.	X		x	X	X	X	X	Х	X
England sites : If patient loses capacity during study, approach Consultee									
Scotland sites : Capacity to be checked at start of study only.									
Informed Consent	Х								
(Informed consent can be given prior to the screening visit but must be confirmed at the screening visit)									
Demographics	X								
Medical History	x		x						
Routine clinical blood	X		X ¹	Х	Х	Х	Х	Х	Х
(Haemoglobin, white cell count, Platelets, APPT, INR/PT, Bilirubin, ALT, Alkaline phosphatase, Total protein, Albumin, Sodium, Potassium, Urea, Creatinine, eGFR, C reactive protein)									

Pregnancy test if child bearing age	X								
Diagnostic ascitic tap (white cell count, neutrophil count and culture)	X		X ¹	X ²					
Eligibility check (inclusion/exclusion)	X		×						
Vital signs	Х		Х	X	Х	X	X	X	Х
(Temperature, blood pressure and pulse)									
(Height and weight at baseline only)									
Liver disease scores (CPS/MELD/UKELD)	x		X	X	X	X	X	X	X
Liver disease assessment and history (includes hepatic encephalopathy, variceal bleeding, ascites and hepatocellular cancer	x		X	x	x	X	X	X	X
Alcohol and substance use assessment (self -reported)	Х		Х	Х	X	X	X	Х	X
Assessment of transport methods available to patient (in case the participant is to travel for LTAD insertion)	X								
Randomisation			Х						
(Can be done up to 10 days prior to the baseline visit)									
Notification of Randomisation		X							
telephone call									
(If randomisation is done prior to baseline visit)									
	1								

Optional Research blood sample 20ml	X						
(10ml for serum, 10ml for whole blood. To be frozen at -80°C for analysis at end of study)							
LTAD/LVP insertion ³	X ³						
Prophylactic antibiotics for both LTAD and LVP groups after discussing risks/benefits	X	X	X	X	X	X	X
Referral to palliative care for both LTAD and LVP groups	X						
LTAD (group 1) research team member to collect drainage data collated by community nurses, also assess LTAD and ask about abdominal pain	X	X	X	X	X	X	X
LVP (group 2) drainage assessment to be collected from medical records.	X	X	X	X	X	X	X
Adverse event review	X	X	X	X	X	X	X

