Concomitant medication review	X	X	X	X	X	X	Х
Ascites questionnaire (Ascites Q) completion (patient)	X	X	X	X	X	X	X
Liver specific HRQoL (SFLDQoL) questionnaire completion (patient)	X		X		Х		X
Generic HRQoL (EQ5D-5L) questionnaire completion (patient)	X	X	X	X	X	X	X
Care giver questionnaire (CRRS) completion (caregiver)	X		X		X		×

Community service use (modified AHCR) questionnaire completion (patient)		X	X	X	Х	Х	Х	Х
Hospital service use in house designed questionnaire completion (research team member)								X
Optional qualitative interviews (patients, informal caregivers and healthcare professionals) will be conducted throughout the study. Only one interview per participant			X	X	X	X	X	X

¹ PT and or INR and platelet count and diagnostic ascitic tap need to be checked within 7 +/-3 days of LTAD insertion; Spontaneous bacterial peritonitis defined as ascitic white cell count > 500 cells/mm³, and or neutrophil count > 250 cells/mm³ and or a positive ascitic fluid culture. (64)

² To be done in LVP group at each drainage as is current standard of care, and LTAD patients only if suspicion for peritonitis. In those with LTAD and clinical suspicion for peritonitis, take ascitic fluid sample for analysis from both from LTAD and via a separate ascitic tap

³ For LTAD only: Prior to LTAD insertion correct INR and platelet count as per local trust guidelines. If no local guidelines available use the following: if INR≥1.5 and platelet count ≤ $50x10^9$ 2 units of Fresh Frozen plasma and 1 -2 pools of platelets to be transfused prior to LTAD insertion

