17.2. Patient Related Outcome Measures (PROMs)

Questionnaires will be completed online if possible (on smart phones), prompted by the fortnightly home visits by the research team members. Participants will also have the option to complete the questionnaires via phone. In those randomised to the LVP group, the questionnaires and fortnightly bloods could also be done in hospital if the LVP visit coincides with assessment visit (+/- 3 days). To further reduce patient and caregiver burden, research team members can assist the participants in completion of the questionnaires if needed and if specifically requested by the participant. If participants are too unwell, the questionnaires can be filled by proxy by the informal caregivers/research team members, both to reduce the patient burden as well as reduce risk of missing data. However, the aim will be to minimise proxy scores if possible. As far as possible informal caregiver is not available during the participant home visit, the questionnaires can be completed at a date and time which is convenient to them, online or over the telephone.

Questionnaires to be used:

SFLDQoL: Liver specific HRQoL assessed at baseline and every four weeks (+/- 3 days). It incorporates a core quality of life assessment and disease-targeted items transformed into the following nine domains on a scale of 0-100 (higher score - better quality of life): distress, stigma, memory, symptoms, sleep, hopelessness, effect of liver disease, loneliness and sexual function. (32) This is completed by the patient and takes 15-20 minutes to complete. Though there was a low completion rates in the feasibility study regarding sexual function questions, this data is important and will still be collected. The research teams will however ensure that questions on sexual function do not need to be answered, if patients feel uncomfortable or reluctant to answer them.

Ascites Q: Ascites symptoms assessed at baseline and fortnightly (+/- 3 days). It is validated in patients with ascites due to cirrhosis. It is a 11-item questionnaire (abdominal pain, fullness, loss of appetite, satiety, nausea, shortness of breath, back pain, mobility, fatigue, sleeping issues, size of abdomen). Each symptom is assessed with a frequency (6-point Likert scale "never" to "always") and discomfort (5-point Likert scale "not at all" to "a lot") question. A higher score indicates more symptoms. (74) This is completed by patients and takes 5-10 minutes to complete.

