23.5. Procedure(s) to account for missing or spurious data

In accordance with MORECare guidance on palliative trials (66), we will summarise attrition in each group as due to mortality, illness and withdrawal. We will assume missing quantitative data to be missing not at random (MNAR) unless there is evidence to the contrary and test results using a range of plausible values. (91-94) If we find evidence of differential attrition, we will, in sensitivity analyses, explore MNAR scenarios by first multiply imputing missing outcomes and then add/subtract (as appropriate) constants from the scores in the most impacted arm and re-estimate the treatment effect. In a systematic review and meta-analysis of 108 palliative trials, there was no evidence of differential attrition related to mortality (95) and we would expect the same in our trial.

Whilst attrition in the feasibility trial (46) was greater in the LTAD arm than in the LVP arm, estimates were imprecise due to the small sample size. The estimated difference in attrition proportions between the two arms was 10.3%, 95% CI (-21.8%, 42.4%). Potential reasons for differential attrition include the contrasting nature of the interventions - participants may prefer to be allocated to LTAD over LVP. Differential attrition may also be due to potential LTAD/LVP related complications. However, our PPI group have stated that the disappointment of being randomised to LVP would be mitigated by the fact that all participants would receive close follow up and fortnightly home visits. Also, irrespective of which arm they were randomised to, participants could take altruistic pride in the fact that they were contributing to the improvement of palliative care for future generations. We will aim to avoid differential attrition. However, if we find evidence of differential attrition, we will, in sensitivity analyses, explore MNAR scenarios e.g. by first multiply imputing missing outcomes and then add/subtract (as appropriate) constants from the scores in the most impacted arm and re-estimate the treatment effect.

23.6. Other Statistical Considerations.

A full statistical analysis plan will be agreed prior to final analysis. Any deviation from this plan will be fully documented in the final trial report.

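### The baseline SFLDQoL that adjusts the primary analysis may be answered after the patient has been randomised and told the arm

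*Protocol*

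**What the plan says.** **Randomisation and disclosure.** Table 3 (section 13.1) marks randomisation at the baseline visit with the note "Can be done up to 10 days prior to the baseline visit", and section 15.5 repeats the allowance: "Randomisation can occur up to 10 days prior to the baseline visit". Section 15.5 continues: "If it occurs prior to the baseline visit, the participants will be informed of their randomisation outcome via a telephone call", and "In this call they will inform patients about which arm of the study they have been allocated to". The baseline column is headed "Baseline / WO (7 +/- 3 days post screening", so the 10-day allowance can reach back as far as screening.

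**First questionnaire.** Section 17.2 has "SFLDQoL: Liver specific HRQoL assessed at baseline and every four weeks (+/- 3 days". Table 3 gives the SFLDQoL four marks, which match weeks 0, 4, 8 and 12, and none at screening. Table 2 and section 17.2 also start the Ascites Q, EQ-5D-5L and CRRS at baseline. Drain insertion is at the same visit (Table 3; sections 16 and 16.2).

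**Order.** Neither the text nor Table 3 puts the questionnaires before randomisation, the telephone call or the drain. The items entered into the randomisation system (section 15.3) are patient ID, site, gender and Child-Pugh score.

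**Use of the score.** Only the trial statistician is blinded (section 15.4). The primary model adjusts for baseline SFLDQoL, and secondary models adjust for the baseline value of their outcome (section 23.4). QALYs are adjusted for baseline utility (section 24). Section 23.1 argues that randomisation makes the expected baseline difference between groups zero.

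**The concern.** Adjusting for a baseline score is safe when allocation cannot have influenced it. A questionnaire answered after a call naming the arm, or after a drain has been placed, does not meet that condition. Several SFLDQoL domains (distress, hopelessness, loneliness) could plausibly respond to such news.

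Suppose patients allocated to LTAD score higher at baseline, or those allocated to LVP score lower, because they know their arm. The model would treat this as a chance imbalance and adjust away part of any LTAD benefit. Worry about an implanted drain would push the estimate the other way. The argument in section 23.1 for a zero baseline difference applies only to a measurement that allocation could not have changed.

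The statistical analysis plan cannot restore a pre-allocation score that was never collected.

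**Working it through.** **Inputs (section 23.1).** Target difference 8 points, SD 26.1, stated effect size 0.31, planning correlation ρ = 0.48 (point estimate 0.77), three follow-ups, 93 per arm analysed, 40% attrition, 310 recruited, 90% power and 5% significance (taken as two-sided).

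**Step 1: the plan's own figure.** For an ANCOVA on the mean of three follow-ups with one baseline and a common correlation, the variance factor is

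f = (1 + 2ρ)/3 − ρ² = (1 + 0.96)/3 − 0.2304 = 0.4229.

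Then n per arm = 2 × 0.4229 × (1.960 + 1.282)² / 0.31² = 92.5, so 93, as stated. The unrounded effect size 8/26.1 = 0.3065 gives 94.6, so 95. The total is 186/(1 − 0.40) = 310. Power at 93 per arm with the unrounded effect is 89.5%. The sample size therefore reproduces, and this point does not dispute it.

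**Step 2: effect of a shifted covariate.** The adjusted difference is (difference in follow-up means) − slope × (difference in baseline means). If knowledge of the arm moves the LTAD-minus-LVP baseline difference by s points and the move does not carry into follow-up, then

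bias = −slope × s, with slope = ρ when SDs are equal and the correlation is common to all visits.

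**Step 3: numbers.** The protocol gives no value for s, so the range below is assumed. The standard error of the adjusted difference is 26.1 × √f × √(2/93). That is 2.49 at ρ = 0.48, and 1.93 at ρ = 0.77 (f = 0.2538). The true effect is set at 8 points. The type I error column sets it at zero.

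| ρ | s | bias | expected estimate | power | type I error |
|---|---|---|---|---|---|
| 0.48 | 0 | 0 | 8.00 | 89.5% | 5.0% |
| 0.48 | 1 | −0.48 | 7.52 | 86% | 5.4% |
| 0.48 | 2 | −0.96 | 7.04 | 81% | 6.7% |
| 0.48 | 4 | −1.92 | 6.08 | 69% | 12.0% |
| 0.77 | 0 | 0 | 8.00 | 99% | 5.0% |
| 0.77 | 1 | −0.77 | 7.23 | 96% | 6.8% |
| 0.77 | 2 | −1.54 | 6.46 | 92% | 12.6% |
| 0.77 | 4 | −3.08 | 4.92 | 72% | 35.9% |

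A negative s inflates the estimate by the same amount. An ANCOVA simulation with 93 per arm agrees: 7.10 and 6.01 at ρ = 0.48 for s = 2 and 4, and 6.48 and 4.95 at ρ = 0.77. Power and type I error refer to the average over the three follow-ups, the quantity for which 93 per arm reproduces.

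**Step 4: can the analysis avoid it?** Dropping the baseline term would remove this bias, but f would rise to (1 + 0.96)/3 = 0.6533. The requirement would become 2 × 0.6533 × (1.960 + 1.282)² / 0.31² = 143 per arm instead of 93.

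**The case against.** **Early randomisation is optional.** A reader might infer that every baseline score is collected after allocation. The protocol does not say so. Randomisation may take place at the visit, the call is made only when it took place earlier, and on the day the questionnaires may come first. The flow chart (Figure 1) is not available here and might show an order. This stands: the score can be post-allocation, but need not be.

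**The protocol does not predict a shift in baseline answers.** Section 23.5 says patients may prefer LTAD and reports the patient group's view that "the disappointment of being randomised to LVP would be mitigated by the fact" of close follow-up. That passage concerns attrition. It makes a reaction to allocation plausible, but it cannot be cited as expecting baseline HRQoL to move.

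**The shift may be small.** The SFLDQoL asks about the last four weeks (Table 1), and a call at most 10 days earlier covers about a third of that period (10/28 = 36%). A reaction in a few domains is diluted across nine. The shift s is also an average over all patients. If half were told early (an assumed share) and only they reacted, an average of 4 points would need 4/0.5 = 8 points in those told, equal to the MCID. The upper end of the range is therefore demanding. These points reduce the likely size without bringing it to zero.

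**A strict gate would do harm.** Section 14.2 says that lack of a caregiver does not bar a patient and that the two need not take part together. Section 17.2 lets patients skip the sexual-function items. Making entry depend on the CRRS, or on a fully completed SFLDQoL, would conflict with both. This stands, and the fix allows for it.

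**Conclusion.** The point holds as a sequencing fault. Followed as written, the plan allows the primary covariate to be an unblinded self-report made after allocation, and nothing in the text or Table 3 prevents it. The same applies to baseline Ascites Q and to baseline utility in the QALY analysis.

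The size and direction of the bias are unknown. An assumed average shift of 1 to 4 points gives 0.5 to 1.9 points at the planning correlation of 0.48, or 6% to 24% of the 8-point target. At 0.77 it gives 0.8 to 3.1 points, or 10% to 39%. These figures assume that the slope equals the correlation and that the shift does not persist into follow-up; a persisting shift would change the bias. The documents do not support a claim that the bias is large, that it favours a particular arm, or that the sample size is wrong. The case for acting is that the lost pre-allocation score cannot be recovered later, while prevention costs little.

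**What to change.** Amend Table 3 and section 15.5 as follows:

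- The patient-reported baseline questionnaires (SFLDQoL, Ascites Q, EQ-5D-5L) are completed after consent and before randomisation. At the minimum, they are completed before the arm is disclosed and before any drain insertion.
- They may be completed at the screening visit, or online or by telephone, routes that section 17.2 already allows. When randomisation is at the baseline visit, the order is questionnaires, then randomisation, then drain.
- Date and time of questionnaire completion, randomisation and disclosure are recorded, so that any departures can be identified in the analysis.
- Sexual-function items may still be skipped. The CRRS is collected before disclosure where a caregiver takes part, but never holds up the patient's randomisation.

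**Cost.** One small amendment, with no extra visit and no extra patients; the total stays at 310. The downside is that questionnaires taken at screening fall 4 to 10 days before the baseline visit (7 ± 3 days). With drainage typically every 10 to 14 days (section 8), some scores, the Ascites Q especially, may then be taken at a different point between drainages. Online or telephone completion shortly before randomisation, or same-day completion in the order above, limits this.
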